**Abstract**

Laser use in dentistry has grown rapidly in recent years. This is especially true for the use of lasers in periodontics. Laser therapy is thought to provide marked improvement in non-surgical treatment outcomes resulting in a reduction in the need for surgery when compared to conventional periodontal therapy (scaling and root planing) alone. The research supporting these claims is limited to a few short-term studies and case reports. Questions remain regarding the long-term benefits of adjunctive laser therapy in the treatment of chronic periodontitis. However, if laser therapy proves to be advantageous, it has the potential to have a significant impact on the treatment of chronic periodontitis. Periodontal health and stability must be demonstrated over time to substantiate the claim of achieving successful periodontal therapy with a reduced need for surgery. The aim of this randomized, controlled clinical study is to examine the clinical efficacy of laser therapy as an adjunct to scaling and root planing in comparison to conventional non-surgical periodontal therapy alone. Clinical parameters including plaque index, gingival index, bleeding on probing, periodontal probing depth and clinical attachment levels will be measured at baseline and at 1, 3, 6, 9, and 12 months following treatment. Intraoral digital periapical radiographs and cone beam computed tomography scans will be taken at baseline, 6 and 12 months to evaluate changes in periodontal bone levels. This non-invasive method of evaluating changes in periodontal bone levels will serve as a surrogate indicator of periodontal bone regeneration.

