**Materials and Methods**

This study will be a single center, prospective randomized, controlled clinical trial. Thirty-Five (35) patients with moderate to severe chronic periodontitis (affecting at least two quadrants, each with two or more sites probing  $\geq 5$ mm) will be included in the study. The research will be conducted in the Postgraduate Periodontics and Implant Surgery Clinic at the UCLA School of Dentistry.

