**CONFIDENTIAL**

---

**Protocol Summary.** Following a thorough review of the patient's health history, clinical and radiographic examination, qualified subjects will sign an informed consent to be enrolled in the study. Treatment will be randomly assigned to quadrants and implemented according to the following standardized protocol:

1. Participants will be provided with oral hygiene aids and receive standardized oral hygiene instructions.
2. One week following oral hygiene instruction participants will return for collection of baseline clinical data including:
  - a. Plaque index
  - b. Gingival index
  - c. Bleeding on probing
  - d. Probing pocket depth
  - e. Gingival recession
  - f. Clinical attachment levels (calculated)
3. Each qualifying quadrant will be randomly assigned to scaling and root planing alone or scaling and root planing with adjunctive laser treatment.
4. At the time of treatment, occlusal contacts will be evaluated and appropriate occlusal adjustments will be made if deemed necessary (i.e. adjustment of occlusal interferences and/or fremitus).
5. Each quadrant will be treated, according to assigned group, at separate visits that are at least two weeks apart.
6. A plaque sample (biofilm) will be collected from selected sites in each qualifying quadrant prior to treatment for microbial analysis. This will be repeated at the re-evaluation appointments.
7. A visual analog scale will be used to assess pain during the first 24-48 hours.
8. Subjects will keep a log of the type and amount of analgesics taken.
9. Subjects will be evaluated at 3, 6, 9 and 12 months after therapy.
10. Periodontal recall maintenance will be provided, as needed, at 3, 6, 9 and 12 months. Oral hygiene instructions will be reinforced at each visit.

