**CONFIDENTIAL**

---

manual soft or extra-soft toothbrush and to use interproximal cleaning aids. Patients will return for postoperative evaluation at week 2 and months 1, 3, 6, 9 and 12.

**Recall Maintenance Cleanings.** Supportive periodontal therapy (recall maintenance cleanings) will be completed, as needed, at 3, 6, 9, and 12 months after treatment. Recall maintenance therapy will be limited to supragingival scaling and prophylaxis.

**Data Collection.** Data will be collected in a standardized, de-identified fashion and will be stored in a locked file cabinet at the study site. Data will be entered into a password-protected database. At the completion of the study including analysis and publication, the data sheets will be destroyed.

**Clinical Measurements.** The following clinical measurements will be recorded at the initial baseline examination (0), 3, 6, 9, and 12 months after treatment:

- Probing depth (PD) at six sites for each tooth
- Bleeding on probing (BOP) at six sites for each tooth
- Plaque index (PI) at six sites for each tooth
- Gingival index (GI) at six sites for each tooth
- Gingival recession at six sites for each tooth
- Clinical attachment level (CAL) at six sites for each tooth (calculated)
- Plaque score % (calculated)
- Bleeding score % (calculated)

**Data Analysis.** A biostatistician will be consulted for data analysis. Comparative evaluation of radiographic imaging will be analyzed with an experienced consultant.

**Patient Compensation.** Subjects will not receive financial compensation for participation in this study. Subjects will be provided with non-surgical periodontal treatment including laser therapy as well as 1 year post-initial therapy maintenance associated with the study at no cost to them. Periodontal therapy will include scaling

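### Does the abstract's month-1 clinical measurement, absent from the Methods, leave the trial's data schedule unsettled?

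*Combined protocol and SAP*

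**What the plan says.** Five places in the protocol bear on the follow-up schedule.

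- **Abstract.** Plaque, gingival inflammation, bleeding, probing depth and attachment level "will be measured at baseline and at 1, 3, 6, 9, and 12 months following treatment".
- **Clinical Measurements** (Materials and Methods). "The following clinical measurements will be recorded at the initial baseline examination (0), 3, 6, 9, and 12 months after treatment". A list of parameters follows, beginning with "Probing depth (PD) at six sites for each tooth".
- **Protocol Summary, item 9.** "Subjects will be evaluated at 3, 6, 9 and 12 months after therapy". No measurement is named here.
- **Post-treatment Instructions.** "Patients will return for postoperative evaluation at week 2 and months 1, 3, 6, 9 and 12".
- **Protocol Summary, item 6**, on the plaque (biofilm) sample taken before treatment. "This will be repeated at the re-evaluation appointments". The appointments are not listed.

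Radiographs are set at baseline, 6 and 12 months in both the Abstract and Protocol Summary item 11. Recall maintenance is set at months 3, 6, 9 and 12 in both Protocol Summary item 10 and the section on recall cleanings.

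**The concern.** A summary may leave out detail, but this one adds a measurement time that the Methods do not have. The addition is not obviously a stray digit either, because a month-1 visit is on the calendar under Post-treatment Instructions. A reader could conclude that the visit was meant for data collection and that the Methods forgot to give it any measurements.

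If so, the first post-treatment clinical data would come at month 3 instead of month 1, and the loss would be permanent. The Hypothesis claims benefit in the short term as well as the long term without defining short term, so the mismatch seems to decide when the earliest comparison can be made. If some patients were charted at month 1 and others not, the data would be patchy at that visit. The plaque sample raises a similar question, since its follow-up appointments are not named.

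**Working it through.** No sample size, power or error rate is involved. The check is a comparison of the schedules, followed by the cost of the larger of the two possible changes.

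**Step 1. Schedules side by side (post-treatment times).**

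| Source | Times | Count | Measurements named? |
|---|---|---|---|
| Abstract | months 1, 3, 6, 9, 12 | 5 | yes |
| Clinical Measurements | months 3, 6, 9, 12 | 4 | yes, full list |
| Protocol Summary, item 9 | months 3, 6, 9, 12 | 4 | no |
| Post-treatment Instructions | week 2, months 1, 3, 6, 9, 12 | 6 | no |

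The Abstract and Clinical Measurements differ by month 1 alone (5 − 4 = 1). Months 3, 6, 9 and 12 appear in all four rows.

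**Step 2. Is an empty month-1 visit a gap?** Week 2 appears in the same sentence as month 1, is also called a postoperative evaluation, and has no clinical measurements in any section. A healing check without six-site charting is coherent. Item 9 and Post-treatment Instructions do differ if read literally, but they are compatible if item 9 refers to the data-collection visits and the other to all visits.

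**Step 3. Does anything depend on month 1?** The Specific Aims name clinical parameters and radiographic bone levels, with no time point. The Hypothesis leaves short term undefined, and month 3 can serve. The Data Analysis paragraph specifies no comparison at month 1. Comparisons of the quadrants at months 3 to 12 need no month-1 value.

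**Step 4. Plaque samples.** If re-evaluation means item 9 of the same numbered list, there are 4 post-treatment samplings. Adding month 1 gives 5. Reaching 6 requires counting the week-2 visit as a re-evaluation, which the protocol nowhere says. The Abstract does not mention these samples, so there is no contradiction here, only unstated detail. The nearest reading is item 9.

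**Step 5. What the two possible changes would do.**

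- *Drop month 1 from the Abstract.* Data collected under the Methods: 4 time points before, 4 after. No result changes.
- *Add month-1 charting.* Five measures are recorded directly (probing depth, bleeding, plaque, gingival index, recession); attachment level and the percentage scores are calculated. Entries per tooth: 5 × 6 sites = 30. The protocol does not give teeth per quadrant, so assume 5 to 7, with only study quadrants charted:
  - two quadrants: 10 to 14 teeth × 30 = 300 to 420 entries per patient; × 35 patients = 10,500 to 14,700;
  - four quadrants: 20 to 28 teeth × 30 = 600 to 840 entries per patient; × 35 patients = 21,000 to 29,400.

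Up to 35 extra visits could also arise (one per patient) if a single month-1 visit was meant to serve both arms, because of the treatment gap in Protocol Summary item 5: "Each quadrant will be treated, according to assigned group, at separate visits that are at least two weeks apart". If follow-up is already timed separately for each arm, the number is 0. That timing question applies equally at months 3, 6, 9 and 12 and is separate from this one.

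**The case for a change.** The strongest case for a change runs as follows. The protocol has no schedule-of-assessments table and no rule on which section prevails, so two careful examiners could act differently at month 1. Recall maintenance starts at month 3 and the protocol does not say whether charting comes before cleaning at that visit, so month 1 is the only disputed time that certainly precedes maintenance. A reader who holds the trial to its Abstract could later see an unreported time point. Correcting the Abstract would cost nothing.

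Some of this stands. The discrepancy is in the text, and tidying it would do no harm. The rest carries less weight. A section that says which measurements are recorded and when is the natural authority over an abstract, and item 9 points the same way. No maintenance visit comes before month 3; only the order of work within that one appointment is open, and adding a month-1 measurement would not settle it. Patchy month-1 charting, if it happened, would be extra data outside the Methods schedule and would leave the records at months 3 to 12 as they are. That missed values cannot be recovered matters only if something needs them, and nothing in the protocol does.

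**Conclusion.** The Abstract and the Methods disagree by one clinical time point out of five, and no change to the plan is called for. Following Clinical Measurements gives a full and sound schedule of baseline plus four follow-up times, with agreement on months 3 to 12 and on the radiographic times. Correcting the Abstract alters no result. Adding month-1 charting is an optional extension, at roughly 300 to 840 entries per patient and 0 to 35 added visits, which a statistician could reasonably decline. The unnamed plaque-sampling visits are a detail that item 9 fills sensibly, and microbial outcomes are not among the Specific Aims.

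This rests on two readings: that the Methods section governs data collection, and that short term in the Hypothesis can be met at month 3. The entry counts also rest on the assumed 5 to 7 teeth per quadrant and on charting the study quadrants only. The conclusion would differ if a month-1 comparison were planned, but the protocol contains none.

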**Background and Significance**

A substantially growing area of interest among clinicians is the use of lasers in the treatment of chronic periodontitis. Recently published data reveals a higher prevalence of periodontal disease in the US population than previously estimated, with approximately half of American adults suffering from varying forms of periodontal disease. Periodontitis is a disease caused by bacterial pathogens that form a biofilm on the tooth / root surface, which elicits a host inflammatory response resulting in bone resorption, attachment loss, pocket formation and/or gingival recession. The diagnosis of periodontal disease is rendered by examination of the supporting tissues with a periodontal probe and evaluation of bone levels with radiographs.

Non-surgical treatment of periodontitis with scaling and root planing (SRP) and ultrasonic scalers has been shown to be effective in removing subgingival calculus and increasing root surface smoothness to aid in the control subgingival bacterial biofilm. As a result, it reduces gingival inflammation, bleeding on probing and probing pocket depths. Oral hygiene instruction with frequent reinforcement is also recognized as an important part of successful treatment. However, SRP alone is not sufficient to treat all cases often due to instrument inaccessibility and clinician skill. It must be noted that significant limitations exist with conventional, non-surgical therapy due to the difficulty in accessing hard to reach areas such as furcations, root concavities, anatomical grooves and deep pockets, which ultimately justifies the need for surgical treatment. Miniaturization and modifications of hand instrumentation have improved our ability to access difficult areas resulting in more effective treatment but challenges remain.

***Surgery vs. Non-Surgical Therapy***

Many studies have addressed the debate of whether to treat periodontitis with surgical or non-surgical methods. While both treatment modalities have been shown to be effective, surgical therapy initially demonstrates better pocket depth reduction in deeper

**CONFIDENTIAL**

---

pockets. This is likely due to the typical access limitations of traditional non-surgical treatment and the inability to effectively remove calculus in deep periodontal pockets.

Recently, lasers have been increasingly promoted as an adjunctive treatment to non-surgical therapy and an alternative to surgical therapy with some studies showing decreases in bacterial load, reduced inflammation and new-attachment/reattachment. Unfortunately, there is a paucity of published clinical studies to evaluate the effectiveness of laser therapy on chronic periodontitis. A significant problem with assessing the effectiveness of laser therapy is the variety of laser types, wavelengths and protocols used for the treatment of periodontal disease. Each laser has a specific medium and operating wavelength. The most common lasers used in dentistry today include the Nd:YAG laser (neodymium doped: yttrium, aluminum, and garnet), the Er:YAG laser (erbium doped: yttrium, aluminum, and garnet), the diode laser and the carbon dioxide (CO2) laser. Wavelengths range from 635 to 10,600 nm. The variability between laser units makes identifying an appropriate and effective protocol difficult. Consequently, numerous questions are raised regarding the efficacy of laser therapy in the treatment of periodontal disease.

The standard of care for the initial treatment of chronic periodontal disease has historically been non-surgical scaling and root planing. Laser therapy may augment non-surgical periodontal therapy by providing improved access to diseased root surfaces, improving the ability to remove calculus and enhance the reduction of oral pathogens found in the periodontal pocket. There may also be a stimulatory effect of laser therapy on periodontal wound healing and regeneration.

*Regeneration vs. Repair*

Studies evaluating conventional periodontal therapy have shown that both periodontal regeneration and repair can result from mechanical therapy and that both can be maintained to achieve stability and health. The question that is of particular interest to many is whether laser therapy has the ability to induce or facilitate periodontal

**CONFIDENTIAL**

---

regeneration. True periodontal regeneration, often considered the ultimate goal in periodontal therapy, occurs when there is regeneration of the periodontal attachment apparatus including new inserting connective tissue fibers into the previously diseased root surface with new cementum, alveolar bone and periodontal ligament.

To date, only two human clinical studies have attempted to evaluate the potential of laser therapy on periodontal regeneration. Specifically, these two studies tested LANAP® (Laser Assisted New-Attachment Procedure), using an FDA approved laser (PerioLase, Millennium Dental Technologies, Inc.) and patented protocol marketed for the treatment of chronic periodontitis. In 2007, Yukna et. al., published human histological results of a small clinical study using the LANAP protocol. Six pairs of single rooted teeth with subgingival calculus in six patients (three men and three women) were scaled and root planed with ultrasonic and hand scalers. One tooth of each pair was also treated with the LANAP® protocol. Three months after treatment, all treated teeth were removed en bloc for histologic processing. The authors reported periodontal regeneration with new cementum and new connective tissue attachment in all six of the LANAP® treated specimens, whereas five of the six control specimens had a long junctional epithelium with no evidence of new attachment or regeneration. In 2012, Nevins, et. al., published histological findings of 10 teeth removed en bloc nine months after treatment with the LANAP® protocol. They reported that five teeth showed evidence of some periodontal regeneration with new cementum, periodontal ligament and alveolar bone. One tooth showed evidence of new attachment with new cementum and inserting collagen fibers, and four teeth showed healing via long junctional epithelium. Critically, there were no controls in this study. Subsequently in 2014, Nevins, et. al., published the nine month clinical findings of the above study. There were eight patients with a total of 930 sites treated with full-mouth LANAP® at a single clinical center. Briefly, the authors reported a mean probing depth reduction from  $4.62 \pm 2.29$  mm to  $3.14 \pm 1.48$  mm after nine months ( $p < 0.05$ ). Recession increased from  $0.86 \pm 1.31$  mm to  $1.52 \pm 1.62$  mm. Analysis revealed that 73% of all sites decreased probing depth, 21% of sites had no change and 6% of sites increased probing depth; 58% of

**CONFIDENTIAL**

---

sites gained attachment, 24% of sites showed no change in attachment and 18% of sites lost clinical attachment. Again, there were only eight patients in the study and there were no controls.

Clearly, well-designed, controlled clinical trials are needed to evaluate the effectiveness of lasers as an adjunctive therapy in the non-surgical treatment of chronic periodontitis.

**Specific Aims**

The purpose of this study is to evaluate whether adjunctive laser therapy will yield more favorable clinical results than conventional therapy alone in the treatment of chronic periodontitis. The laser to be evaluated in this study is the Waterlase iPlus (Er,Cr:YSGG) laser.

The specific aims of this research are to:

1. Evaluate the effect of adjunctive laser (Er,Cr:YSGG) therapy on periodontal disease resolution using clinical parameters to assess improvement in periodontal health.
2. Evaluate the effect of adjunctive laser (Er,Cr:YSGG) therapy on periodontal regeneration using radiographic imaging to assess changes bone levels (as a surrogate marker of regeneration).

**Hypothesis**

Laser therapy, used as an adjunctive treatment with conventional non-surgical therapy, improves the short- and long-term clinical and radiographic results of periodontal treatment as compared to conventional non-surgical therapy alone and reduces the need for surgical intervention in patients with moderate to severe chronic periodontitis.

**Materials and Methods**

This study will be a single center, prospective randomized, controlled clinical trial. Thirty-Five (35) patients with moderate to severe chronic periodontitis (affecting at least two quadrants, each with two or more sites probing  $\geq 5$ mm) will be included in the study. The research will be conducted in the Postgraduate Periodontics and Implant Surgery Clinic at the UCLA School of Dentistry.

**Inclusion criteria**

- Age 18 years old or older (male or female)
- Healthy without systemic diseases that may adversely effect healing
- Not pregnant and no current plans to become pregnant
- No periodontal treatment in the previous 6 months
- No systemic antibiotic therapy in the previous 6 months
- At least two quadrants with chronic periodontitis (ideally opposite side same jaw)
- Each quadrant must have two or more sites with probing pocket depths  $\geq 5$ mm
- Presence of interproximal intrabony defect(s) in each quadrant

**Exclusion criteria**

- Any systemic disease, medication, or habit known to adversely influence bone metabolism and/or wound healing:
  - o Poorly controlled diabetes (HbA1c  $> 7\%$ )
  - o History of bisphosphonate medications
  - o History of radiation therapy affecting the proposed treatment site(s)
  - o History of immunosuppressive medications (e.g. corticosteroids)
  - o History of tobacco use (current or past tobacco use within the past 1 year)
  - o Immune compromise caused by disease, treatment or other condition
- Recent history of periodontal surgery (within the previous 2 years)
- Recent history of scaling and root planing (within the previous 1 years)
- Any condition that contraindicates periodontal therapy including surgery

**CONFIDENTIAL**

---

**Instrumentation.** The laser to be used in this protocol is the Waterlase iPlus Er,Cr:YSGG laser manufactured by Biolase (Irvine, California, USA).

Laser specifications as described by the manufacturer:

- Model: Waterlase iPlus
- Operating Voltage: 100 VAC  $\pm$  10% / 230VAC  $\pm$  10%
- Frequency: 50 / 60 Hz
- Current Rating: 15.0 A / 8A
- Laser classification: Class 4 (Er,Cr:YSGG), Class 1 (635nm red Aiming Beam)
- Type of laser: Er,Cr:YSGG
- Wavelength: 2780 nm
- Type of operation: Pulse
- Laser energy: 0- -600 mJ
- Aiming Beam: 635nm (red)
- Cooling method: Water cooling (built-in reservoir)
- Outer dimensions (WxDxH): 11" x 19" x 33" (246mm x 585mm x 1057mm)
- Weight: Approx. 75 lb. (34 kg)

**Operator training.** A training session offered by Biolase and The World Congress for Laser Instruction (WCLI) for the use of the Waterlase iPlus Er,Cr:YSGG laser has been completed by the principal investigator and will be completed by all co-investigators participating in this study.

A pressure sensitive Florida Probe will be used to standardize and calibrate examiners. A UNC-15 periodontal probe will also be used in this study to evaluate the clinical parameters. It has markings in 1 mm increments up to 15 mm.

Non-surgical instrumentation will include the use of a Symmetry IQ 3000 Piezo Scaler (Hu-Friedy) with fiber optic light and various tips, Universal and Gracey curettes (Hu-Friedy).

